3 DESIGN

3.1 Study Design

This is a Phase 2 Double Blinded and Placebo Controlled Study evaluating the safety, pharmacokinetics, and efficacy of favipiravir in adult subjects with PCR-positive, asymptomatic, or mild COVID-19 infections.

Subjects will be randomized to receive either favipiravir + current local Standard of Care (SOC) or placebo + SOC. SOC at Stanford is defined as methods Stanford University Healthcare is using for COVID-19 patients at the time of study initiation. Each site's local SOC to be defined and shared with Sponsor prior to study initiation.

For those subjects in the favipiravir + SOC arm, the dose regimen will be 1800 mg BID favipiravir on the first dose (day 1) followed by 800 mg BID for the next 9 days (days 2-10). NOTE: 600 mg BID for subjects with Child-Pugh A liver impairment on days 2-10.

Subjects in the SOC arm will receive placebo. The total anticipated duration of the study for each patient is 28 days.

3.2 Study Sites

This study is being supported by the Stanford Innovative Medicines Accelerator (IMA), Clinical Trials Research Unit (CTRU), and the Stanford Center for Clinical Research. This study may be performed at up to 5 sites nationally.

Each investigator or group of investigators at a clinical site must obtain Institutional Review Board (IRB) approval for this protocol and submit all required regulatory documents (including any protocol specific documents) to their respective IRB as required per institution. Sites can submit through a Stanford-designated central IRB for this trial. All subsequent mentions of IRB related activity in this document will reflect whichever choice they decide, be it local or central IRB.

Requirements for site selection and site registration: Sites will be evaluated by Stanford team and the main PI prior to selection or activation.

Stanford requires documentation that verifies IRB-approval for this protocol, informed consent documents, and associated documents prior to recruitment, screening, and enrollment of subjects, and any IRB-approvals for continuing review or amendments.

Please refer to the MOP for information on:

- Requesting and submitting regulatory documents
- Patient enrollment & randomization
- Randomization notification
- Requesting study drug
- Withdrawals
- Lost to follow-up
- Protocol deviations
- Data submissions

4 OBJECTIVES

4.1 Primary Objective

To evaluate the efficacy of oral favipiravir plus SOC compared with placebo plus SOC in reducing the duration of shedding of SARS-CoV2 virus in patients with mild or asymptomatic COVID-19 disease.

4.2 Secondary Objectives

1. To evaluate the efficacy of oral favipiravir plus SOC compared with placebo plus SOC in reducing the duration of symptoms, hospitalizations, or ED visits in patients with mild or asymptomatic COVID-19 disease.
2. To assess the safety and tolerability of favipiravir in this subject population.
3. To assess the development of antibodies against SARSCoV-2
4. To evaluate any changes in the PK profile of favipiravir and its major metabolite M1 in this subject population
5. To determine the viral load and duration of viral shedding in stool as measured by RT-PCR.

6. To characterize microbiome signatures of infection by next-generation sequencing.

5 SUBJECT POPULATION

5.1 Inclusion Criteria

The following criteria must be confirmed as “YES” except optional PK, antibody, and stool sample collection:

1. Adults (18 to 80 years old inclusive)
2. Diagnosis of COVID-19 disease:
 - a. If symptomatic without signs of respiratory distress (as defined by SpO₂ \geq 94% on room air, RR \leq 20, HR \leq 100), with FDA-cleared molecular diagnostic assay positive for SARS-CoV-2 within 72 hours from swab to the time of commencing informed consent. Mild disease is defined as having at least 1 of the following:
 - i. Fever ($>98.7^{\circ}\text{F}$)
 - b. Cough/Shortness of breath/dyspnea
 - c. Fatigue
 - d. Headache/Body aches
 - e. Joint pain
 - f. Chest pressure
 - g. GI symptoms including nausea, vomiting, and/or diarrhea
 - h. Abdominal pain
 - i. Sore throat
 - j. Nasal congestion
 - k. Chills
 - l. Runny nose
 - m. New loss of taste or smell
 - n. Abdominal pain
 - o. Rash
 - p. If asymptomatic, initial diagnosis obtained no more than 72 hours from initial swab to the time of commencing informed consent
3. Subject or their legal representative understands the requirements of the study and provides written informed consent prior to undergoing any treatment-related procedures.
4. Subject agrees to take daily nasal swabs (anterior nares) for Day 1 to Day 10 and Day 14, 21, and 28 using the study provided materials, and mail via FEDEX each sample on the day collected.
5. Subject agrees to record daily symptoms, temperature, oxygen saturation, and pulse using the study provided materials.
6. Subject agrees to obtain stool samples after the Day 1 visit, and 1-3 days before the Day 14 and Day 28 timepoints and agrees to bring the sample back in the provided stool collection kit to their subsequent appointment and to optionally mail in 4-month sample. Collection of stool is optional for sites.
7. Subject agrees to return to the study site for follow-up visits on Day 5, 10, and 28. The study site will be staffed by trained healthcare providers wearing full personal protective equipment and study site equipment will be disinfected between patients according to the same protocols

as a clinical setting. Subjects will be wearing masks, will be appropriately spaced, and the number of subjects assessed at each time will be limited.

8. Subject agrees to maintain home or other quarantine as recommended by the study physician, except to visit the study site as required by the protocol.
9. Members of the same household may participate in the study as long as the inclusion and exclusion criteria are met.
10. If male, subject must:
 - a. Be sterile (e.g., have had a vasectomy at least 6 months prior to Day 1 dosing), OR,
 - b. Agree not to donate sperm during the study and for seven days following the last dose of study medication, AND,
 - c. Agree to strictly adhere to the following contraceptive measures during the study and for seven days following the last dose of study medication:
 - i. Abstain from sexual intercourse.
 - ii. Use a condom during sexual intercourse with a female of child-bearing potential. In addition, the female partner must use another form of contraception (e.g. intrauterine device [IUD], diaphragm with spermicide, oral contraceptives, injectable progesterone, or subdermal implants).
11. If female, subject must:
 - a. Be unable to bear children (have not had a period for ≥ 12 consecutive months, have had her uterus or ovaries removed, or have had a tubal ligation), OR,
 - b. Must ensure that their male partner is incapable of fathering a child (e.g., has had a vasectomy at least 6 months prior to study entry), OR,
 - c. If she is of childbearing potential will strictly adhere to the following contraceptive measures during the study and for seven days following the last dose of study medication:
 - i. Abstain from sexual intercourse, OR,
 - ii. Must ensure that her male partner agrees to use a condom during sexual intercourse and agree to use an approved method of contraception (e.g., IUD, diaphragm with spermicide, oral contraceptives, injectable progesterone, or subdermal implants).
 - d. Agrees to stop breast-feeding prior to first dose of study drug and through seven days after completing therapy.
 - e. Has a negative urine pregnancy test at screening.
 - f. Has not had unprotected sexual intercourse within the past month.

5.2 Exclusion Criteria

All criteria must be confirmed as “NO”:

1. Subject has a concomitant bacterial respiratory infection, as defined by positive respiratory culture
2. Subject has a history of abnormalities of uric acid metabolism unless cleared
3. Subject has a history of hypersensitivity to an anti-viral nucleoside-analog drug targeting a viral RNA polymerase
4. Subject has any of the following abnormal laboratory test results at screening:
 - a. Platelet count $<100,000$ cells/mm³
 - b. Absolute lymphocyte count <500 cells/mm³

- c. Hemoglobin <11 g/dL for women and <12 g/dL for men
 - d. Serum creatinine concentration $\geq 1.5 \times$ ULN
 - e. Confirmed creatinine clearance (CrCl) < 50 mL/min by Cockcroft-Gault
 - f. Serum uric acid >20mg/dL
5. Subject is using adrenocorticosteroids (except topical or inhaled preparations or oral preparations equivalent to or less than 10 mg of oral prednisone) or immunosuppressive or immunomodulatory drugs (e.g., immunosuppressants, anticancer drugs, interleukins, interleukin antagonists or interleukin receptor blockers).

NOTE: Treatment of study participants following institutional COVID-19 treatment policies or guidelines, including the use of immunomodulatory medications, is permitted. This excludes treatment with agents that have the potential for direct antiviral activity, including convalescent plasma and NO, and co-enrolment into other clinical studies that evaluate investigational agents for COVID-19.

6. Subject has a serious chronic disease (e.g., human immunodeficiency virus [HIV], cancer requiring chemotherapy within the preceding 6 months, moderate or severe hepatic insufficiency and/or unstable renal, cardiac, pulmonary, neurologic, vascular, or endocrinologic disease states per investigator judgement).
7. Has previously received favipiravir within the past 30 days.
8. Has renal insufficiency requiring hemodialysis or continuous ambulatory peritoneal dialysis (CAPD).
9. Has liver impairment greater than Child-Pugh A. (NOTE: Child-Pugh A subjects will have the maintenance dose decreased to 800 mg BIID).
10. Has a history of alcohol or drug abuse in the previous 6 months.
11. Has a psychiatric disease that is not well controlled where controlled is defined as: stable on a regimen for more than one year.
12. Has taken another investigational drug within the past 30 days.
13. Is deemed by the Investigator to be ineligible for any reason.

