
Individual Stopping Rule
	
A subject should be removed from favipiravir treatment if one of the following criteria is met:
 
 • AST or ALT > 8 x ULN • ALT or AST > 3 x ULN AND total bilirubin > 2X ULN • AST or ALT > 3 x ULN AND patient has right upper quadrant pain or eosinophilia

	
 • Uric acid >20mg/dL 
A subject whose treatment is terminated should remain in the study for appropriate follow up assessments.

Study Measurements: Efficacy, Safety and PK
	
Primary Measurement (Efficacy):
 
 1. Time to first of two negative tests based on nasal swab for RT-PCR taken daily from Day 1 to Day 10, and Days 14, 21, and 28. 
Secondary Measurements (Safety, Efficacy and PK):
 
 2. Oropharyngeal swab for nucleic acid (RT-PCR) taken Day 1, 5, 10, and 28. 3. Symptom improvement or worsening: Subjects will fill in a diary daily, recording the following symptoms: 
 a. Cough b. Sore throat c. Headache d. Nasal congestion e. Body aches and pains f. Fatigue g. Oral temperature taken after 4 pm and at least four hours after ingesting the most recent antipyretic (acetaminophen or NSAID) h. Dyspnea i. Shaking chills j. New loss of taste or smell k. GI symptoms including nausea, vomiting, and/or diarrhea l. Chest pain 4. Safety as assessed by: 
 a. Observed and reported adverse events b. Clinical laboratory evaluations of blood on Days 1, 5, 10, and 28 c. Physical Examination at screening (pre-dose Day 1), Days 10, and 28 d. Daily vital signs: pulse oximetry, heart rate, and temperature. 5. Optional Blood for determination of antibodies to SARS-CoV-2 will be obtained on Days 1 and 28. Collection of blood for antibodies is optional for sites. 6. Optional Blood for PK obtained pre-dose (within 30 minutes prior to dosing) and post-dose (45 to 75 minutes following dosing) on Days 1, 5 and 10. Collection of PK is optional for sites. 7. Optional Stool samples for determination of viral load in stool and microbiome characterization will be obtained in the following

	windows Day 1±5, 14±7, and 28±7. Collection of stool is optional for sites.
--	---

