5.3 Removal of Subjects from Treatment

The participation of a subject in the study or the administration of treatment may be terminated at any time for one of the following reasons:

- The subject desires to discontinue study treatment.
- The subject withdraws consent to participate in the study.
- The subject is unwilling or unable to comply with the safety procedures.
- The subject is discovered to be pregnant.
- The subject experiences a medical emergency that necessitates withdrawal.
- The subject is withdrawn at the discretion of the Investigator for medical reasons or non-compliance.
 - AST or ALT > 8 x ULN
 - ALT or AST > 3 x ULN AND total bilirubin > 2X ULN
 - AST or ALT > 3 x ULN AND patient has right upper quadrant pain or eosinophilia

- Uric acid >20mg/dL CrCl < 30

A subject whose treatment is terminated should remain in the study for appropriate follow up assessments whenever possible.

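### The exclusion lists set no AST, ALT or bilirubin limit, although three of the laboratory removal criteria are hepatic: a cheap consistency gap to close

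*Combined protocol and SAP*

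**What the plan says.** **Entry.** Section 5.2 item 4 opens with "Subject has any of the following abnormal laboratory test results at screening" and lists six limits: platelets, lymphocytes, hemoglobin, serum creatinine, creatinine clearance (CrCl) and uric acid. Synopsis item 14 repeats them. The liver enters eligibility only through criteria that carry no AST, ALT or bilirubin value:

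- exclusion 6, which gives moderate or worse hepatic insufficiency as an example of serious chronic disease;
- exclusion 9, for impairment beyond Child-Pugh A;
- exclusion 13, the catch-all "Is deemed by the Investigator to be ineligible for any reason".

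**Stopping.** The synopsis rule reads "A subject should be removed from favipiravir treatment if one of the following criteria is met". Section 5.3 is softer: "the administration of treatment may be terminated at any time for one of the following reasons", with the laboratory values listed beneath the reason that refers to the investigator's discretion. Both places give the same three hepatic criteria. One of them is "ALT or AST > 3 x ULN AND total bilirubin > 2X ULN".

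**After stopping.** Section 5.3 says "A subject whose treatment is terminated should remain in the study for appropriate follow up assessments whenever possible". Section 9.4 puts every randomised patient in the ITT population and bases all efficacy analyses on it.

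**Timing of tests.** Section 7.1 places the chemistry and hematology bloods in the Day 1 pre-dose list, ahead of the randomisation step. Footnote A to the Section 14 schedule accepts liver function results from within 48 hours of enrollment.

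**The concern.** A value that the plan names as a reason to stop treatment should normally be a reason not to start it. The plan follows that principle for kidney function and uric acid but not for the liver. A person with a qualifying liver result at screening can therefore satisfy every numeric entry limit.

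Neither removal rule is restricted to values obtained after baseline, so it could be applied to that same screening result. If it is, the person has been randomised for little or no treatment and still counts in the ITT analysis. If it is not, the person is treated while above a threshold that the sponsor chose as a reason to stop. Either way this is an avoidable inconsistency in who may be dosed.

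**Working it through.** The plan states no figure on this point, so there is none to reproduce. The check sets the removal limits beside the entry limits.

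| Laboratory reason to stop | Where stated | Entry limit (5.2 item 4; synopsis item 14) |
|---|---|---|
| Uric acid above 20 mg/dL | Synopsis and 5.3 | Same threshold |
| CrCl below 30 | 5.3 only | Stricter: below 50 mL/min |
| AST or ALT above 8 x ULN | Synopsis and 5.3 | None |
| AST or ALT above 3 x ULN, bilirubin above 2 x ULN | Synopsis and 5.3 | None |
| AST or ALT above 3 x ULN, with right upper quadrant pain or eosinophilia | Synopsis and 5.3 | None |

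The six entry limits and the five removal limits were then coded as rules and applied to hypothetical subjects who were otherwise normal:

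| Subject | Excluded by item 4? | Meets a removal limit? |
|---|---|---|
| ALT 9 x ULN | No | Yes |
| ALT 4 x ULN, bilirubin 2.5 x ULN | No | Yes |
| AST 4 x ULN, right upper quadrant pain | No | Yes |
| Uric acid 21 mg/dL | Yes | Yes |
| CrCl 25 mL/min | Yes | Yes |

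This tests the numeric limits only. It shows that the number is missing; it does not show that an investigator using exclusions 6, 9 or 13 would let these subjects in.

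**Size per subject.** Planned enrollment is 90 per arm and 180 in total. One subject is 1/90 = 1.1% of an arm, or 1/180 = 0.6% of all randomised. The documents give no rate of abnormal liver tests at screening, so no count can be derived.

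**Exposure, favipiravir arm only.** Section 3.1 gives the regimen as "1800 mg BID favipiravir on the first dose (day 1) followed by 800 mg BID for the next 9 days (days 2-10" (days 2 to 10).

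- Full course: 2 x 1800 + 9 x 2 x 800 = 3600 + 14,400 = 18,000 mg.
- Result acted on before the first dose: 0 mg.
- After one loading dose: 1800/18,000 = 10.0%.
- After both loading doses: 3600/18,000 = 20.0%.

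The documents do not say when the liver results come back, so these three cases are a range and not a forecast.

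**The case against.** The strongest reply is that the gap is largely covered in practice. Exclusions 6 and 9 remove the more serious liver disease, and exclusion 13 lets the investigator refuse anyone. Liver status has to be considered at entry in any case, because Child-Pugh A subjects get a modified dose; the exclusion 9 note says "Child-Pugh A subjects will have the maintenance dose decreased to 800 mg BIID". (Sections 3.1 and 6.1 say 600 mg; that conflict is a separate matter.) An investigator who sees ALT above 8 x ULN is unlikely to enrol the person and then stop treatment on the same value. This stands as a reason to expect few cases or none. It does not close the gap: none of the three exclusions gives a liver test threshold, and exclusion 13 would equally make the six written limits unnecessary, yet the sponsor wrote those.

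Three stronger readings are tempting, and the documents do not support them.

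- *Such a subject is randomised only to be stopped.* Only the synopsis says *should*; Section 5.3 says *may*. Stopping is possible but not certain.
- *Such a subject would be dosed unnoticed until the Day 5 bloods.* That would be 3600 + 3 x 1600 = 8400 mg, or 46.7% of the course. The plan directs nothing of the kind. Section 7.1 schedules the chemistry pre-dose and before randomisation, and it also requires a medical history, a physical examination and a baseline symptom survey. What is missing is a criterion to read those results against.
- *The primary comparison is biased or diluted.* With an unknown and possibly zero count, nothing in the documents supports a material effect on the hazard ratio. They also describe no liver signal for favipiravir from which to claim a particular level of risk.

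**Conclusion.** The point holds as a cheap improvement in safety and consistency. All three hepatic removal criteria lack an entry counterpart, while both non-hepatic laboratory removal limits have one that is equal or stricter. Unless exclusion 6, 9 or 13 is applied by judgement, a person who already meets a hepatic removal criterion at screening is eligible and may be randomised and dosed.

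This rests on two readings of the text: that the removal rules can apply to a screening value, since neither place limits them to later ones, and that the non-numeric exclusions do not oblige an investigator to refuse an isolated transaminase rise. If the sponsor intends the removal rules for on-treatment values only, the protocol should say so, and it would then be accepting that treatment can start above its own stopping threshold.

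**What to change.** Add one item to Section 5.2 item 4 and to synopsis item 14: screening results that meet any hepatic criterion in Section 5.3, namely AST or ALT >8 x ULN; AST or ALT >3 x ULN with total bilirubin >2 x ULN; or AST or ALT >3 x ULN with right upper quadrant pain or eosinophilia. State in Section 7.1 that the pre-dose chemistry, differential and baseline symptom results already scheduled are reviewed against this item before randomisation.

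No new test is needed: AST, ALT, total bilirubin and the differential are in the Section 8.4 panel. The cost is a protocol amendment with IRB review, a change to the eligibility form, and possibly a few extra screen failures. Liver results would have to be back before randomisation, as the creatinine and blood-count limits already require for theirs.

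The added item would still admit an isolated AST or ALT up to 8 x ULN. A stricter limit is a clinical choice for the sponsor. The documents give no cut-off for eosinophilia; that is a separate missing detail in the removal rule, which the new item would inherit until it is defined.

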1 SYNOPSIS

Title	A Phase 2 Randomized, Double Blinded, Placebo Controlled Study of Oral Favipiravir Compared to Current Standard of Care in Subjects with Mild or Asymptomatic COVID-19
Design	
This is a Phase 2 Double Blinded, Placebo Controlled Study evaluating the efficacy, safety and pharmacokinetics of favipiravir in adult subjects with PCR-positive, mild or asymptomatic COVID-19 infections. The study is a multicenter trial that will be conducted in up to 5 sites nationwide.
 
Subjects will be randomized to receive either favipiravir + current Standard of Care (SOC) or placebo + SOC.
 
For those subjects in the favipiravir + SOC arm, the dose regimen will be 1800 mg BID favipiravir on the first dose (day 1) followed by 800 mg BID for the next 9 days (days 2-10).
 
NOTE: 600 mg BID for subjects with Child-Pugh A liver impairment on days 2-10.
 
Subjects in the SOC arm will receive placebo.
 
The total anticipated duration of the study for each patient is 28 days.

Objectives	
Primary Objective
 
To evaluate the efficacy of oral favipiravir plus SOC compared with placebo plus SOC in reducing the duration of shedding of SARS-CoV2 virus in patients with mild or asymptomatic COVID-19.
 
Secondary Objectives
 
 1. To evaluate the efficacy of oral favipiravir compared with placebo in reducing the onset or duration of symptoms, hospitalizations, or ED visits in patients with mild or asymptomatic COVID-19. 2. To assess the safety and tolerability of favipiravir in this subject population. 3. To assess the development of antibodies against SARS-CoV-2 4. To evaluate any changes in the PK profile of favipiravir and its major metabolite M1 in this subject population
Endpoints	
Primary Endpoint:
 
Time until cessation of shedding of SARS-CoV-2 virus, defined as the time in days from randomization to the first of two consecutive negative RT-PCR results of self-collected nasal swabs.
 
Secondary Endpoints
 
 1. Nucleic acid (RT-PCR) from oropharyngeal swabs collected on Days 1, 5, 10, and 28

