	
less than 10 mg of oral prednisone) or immunosuppressive or immunomodulatory drugs (e.g., immunosuppressants, anticancer drugs, interleukins, interleukin antagonists or interleukin receptor blockers).
 
NOTE: Clinical screening laboratory evaluations will be performed locally by the site or site-designated laboratory. Treatment of study participants following institutional COVID-19 treatment policies or guidelines, including the use of immunomodulatory medications, is permitted. This excludes treatment with agents that have the potential for direct antiviral activity, including convalescent plasma and NO, and co-enrolment into other clinical studies that evaluate investigational agents for COVID-19.
 
 15. Subject has a serious chronic disease (e.g., human immunodeficiency virus [HIV], cancer requiring chemotherapy within the preceding 6 months, and/or moderate or severe hepatic insufficiency and/or unstable renal, cardiac, pulmonary, neurologic, vascular, or endocrinologic disease states per investigator judgement). 16. Has previously received favipiravir within the past 30 days. 17. Has renal insufficiency requiring hemodialysis or continuous ambulatory peritoneal dialysis (CAPD). 18. Has liver impairment greater than Child Pugh A. 19. Has a history of alcohol or drug abuse in the previous two years. 20. Has a psychiatric disease that is not well controlled where controlled is defined as: stable on a regimen for more than one year. 21. Has taken another investigational drug within the past 30 days. 22. Is deemed by the Investigator to be ineligible for any reason.

Randomization
	
Following consent, those subjects meeting all entry criteria will be randomized in a 1:1 ratio.
 
Treatment Arm: favipiravir + SOC
 
Control Arm: placebo + SOC
 
Randomization will be stratified by age (≥ 50 and < 50 years old) and sex.

Treatment Regimen for Favipiravir (Standard dose)
	
 • Favipiravir and placebo tablets will be administered orally. • The regimen begins with loading doses of 1800 mg BID on Day 1 (the first 24 hours of treatment at $t = 0$ and $t = 8-12$ hours) (3600

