	
mg/day). Then maintenance dosing of 800 mg BID (1600 mg/day) from Day 2 (beginning 18-24 hours after the loading dose on Day 1).
 
 • Patients with Child-Pugh liver impairment of grade A will have their maintenance dose decreased to 600 mg BID • The total duration of treatment is expected to be 10 days.

Duration of Study Participation
	
The total anticipated duration of the study for each patient is up to 28 days.

Statistical Methods
	
To address our primary objective, time until viral shedding cessation will be compared between the two treatment arms using a two-sided Wald test derived from a Cox proportional hazards model adjusted for age and sex and stratified by site. The test will be performed at the two-sided $\alpha = 0.05$ level of significance. The hazard ratio for shedding cessation will be estimated, along with its 95% confidence interval, from a Cox proportional hazards model. If the proportional hazards assumption is not met, we will consider an extended Cox model that relaxes the proportional hazards assumption. The log rank test will also be performed.
 
The distribution of viral shedding cessation will be estimated using the Kaplan-Meier method, and Kaplan-Meier curves will be presented for each treatment arm. Time to shedding cessation along with 95% confidence intervals will be presented for each treatment arm.
 
The rate of hospitalizations and ED visits will be estimated along with 95% confidence intervals by each arm. In addition, we will compare between arms the time to each of respiratory failure, hospitalization or deaths and the corresponding composite of all such events using Kaplan-Meier methods. The frequency of adverse events and serious adverse events will be tabulated by type and by treatment arm. AEs will be compared by arm using the Chi-squared test or Fisher’s exact test, as appropriate, in the safety analysis set.
 
An interim analysis for safety and overwhelming efficacy will be performed once 50% of patients have 24 hours of follow-up complete. Enrollment will pause once 50% of patients have received treatment and will remain paused until the DSMC makes their recommendation after their safety review.

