6 STUDY TREATMENT - FAVIPIRAVIR

6.1 Study Drug

Favipiravir will be provided in 200 mg tablet form to be stored at controlled room temperature (15°C to 30°C [59°F to 86°F]) and shielded from light. Matching placebo will be provided in tablet form to be stored at controlled room temperature (15°C to 30°C [59°F to 86°F]) and shielded from light.

Standard Dose

Subjects randomized to the favipiravir + SOC arm will be administered loading doses of 1800 mg BID (ideally 12 hours apart but 10-16 hours is allowed) on Day 1, and then maintenance dosing of 800 mg twice daily BID (Ideally 12 hours apart but 10- 16 hours is allowed) on Days 2-10 beginning 24 hours after the first dose. Day 1 is deemed to be the first 24 hours after enrollment into the study, with time 0 (time of first dose) occurring as soon as possible after the subject's eligibility has been confirmed.

An exception to the above maintenance dose will be made for those subjects entering the study with a Child-Pugh liver impairment of grade A who will receive favipiravir 600 mg BID on Days 2 through 10.

Subjects randomized to the placebo + SOC arm will be administered placebo BID (ideally 12 hours apart but 10-16 hours is allowed) on Day 1, and then maintenance dosing twice daily BID (Ideally 12 hours apart but 10- 16 hours is allowed) on Days 2-10 beginning 24 hours after the first dose. Day 1 is deemed to be the first 24 hours after enrollment into the study, with time 0 (time of first dose) occurring as soon as possible after the subject's eligibility has been confirmed.

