6.6 Treatment Precautions

An overdose is defined as any dose of study drug given to a subject or taken by a subject that exceeds the dose described in this document. In the event of an overdose, the subject should be treated symptomatically, and the Sponsor informed.

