7.1 Day 1 (PRE-DOSE)

- Obtain informed consent.
- Verify eligibility per the inclusion and exclusion criteria. (See Sections 5.1 and 5.2)
 - Review and record medical history, including tobacco use, to ensure there are no exclusionary illnesses.
 - Review and record concomitant medications for possible prohibited medications. (See Section 6.7)
- If subject is female of child-bearing potential and meets inclusion criteria 11.c, obtain urine pregnancy test and proceed if result is negative.
- Measure and record vital signs (BP, HR, Temp, Resp).
- Collect and record SPO2 by Finger Sensor
- Perform Physical exam (may be done by the Principal Investigator or their designee)
- Complete baseline symptom survey to establish severity of symptoms (if present)
- Collect oropharyngeal swab for virologic testing (RT-PCR) and resistance analysis.
- Collect two nasal swabs for antigen testing and molecular viability testing.
- Collect blood samples for
 - Uric acid
 - CRP
 - Hematology and clinical chemistry laboratory analyses (samples collected within 48 hours of enrollment are acceptable):
 - Resistance analysis
 - Optional: Antibodies to SARS-CoV-2.
 - Optional: Biobanking
 - Optional: Pre-dose PK

- Perform subject randomization (via EDC) to establish treatment arm (favipiravir + SOC or placebo + SOC).
- Explain in home procedures for the study (self-sampling of nasal swabs, temperature, SPO2, completing the daily questionnaire and the optional collection of stool sample).
- Provide supplies to research subject and review the calendar of return visits.
- Optional: Explain that stool sample from first bowel movement after enrollment should be collected in Zymo fecal tube and brought back to Day 5 follow-up visit. If the first bowel movement sample cannot be collected, it is permitted to collect a subsequent bowel movement sample.

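### The note to exclusion criterion 9 in Section 5.2 sets the Child-Pugh A maintenance dose at 800 mg BID, the standard dose, where the synopsis, 3.1 and 6.1 give 600 mg BID

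*Combined protocol and SAP*

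**What the plan says.** The standard favipiravir regimen is 1800 mg BID on Day 1, then 800 mg BID on Days 2-10 (synopsis, 3.1 and 6.1). The synopsis Treatment Regimen row also states the maintenance total as 1600 mg/day.

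Only impairment beyond Child-Pugh A is excluded. Synopsis exclusion 18 reads "Has liver impairment greater than Child Pugh A" and has no dose note. Section 5.2, criterion 9, is the same criterion with a note added: "Child-Pugh A subjects will have the maintenance dose decreased to 800 mg BIID".

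The Child-Pugh A maintenance dose is stated in four other places:

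- Synopsis, Design row: "600 mg BID for subjects with Child-Pugh A liver impairment on days 2-10".
- Synopsis, Treatment Regimen row: "Patients with Child-Pugh liver impairment of grade A will have their maintenance dose decreased to 600 mg BID".
- Section 3.1: "NOTE: 600 mg BID for subjects with Child-Pugh A liver impairment on days 2-10".
- Section 6.1, for patients entering with grade A impairment: "who will receive favipiravir 600 mg BID on Days 2 through 10".

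Section 6.6 defines an overdose as "any dose of study drug given to a subject or taken by a subject that exceeds the dose described in this document".

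**The concern.** A dose cannot be decreased to the value it already has. The note sits beside the criterion that staff consult when they judge liver status: Section 7.1 sends them to 5.1 and 5.2 to confirm eligibility on Day 1. The study may run at up to 5 sites, each reading the text for itself. A site that took the dose from the note would give a liver-impaired patient the full maintenance dose for nine days and could still point to the protocol as its authority. What is at stake is dosing safety and protocol adherence in a small subgroup. Sample size, power and alpha are not involved.

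**Working it through.** **Can another reading remove the conflict?**

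- The note might mean a decrease from the 1800 mg loading dose. It does not: it names the maintenance dose.
- The note might give 800 mg as a daily total, with BIID as a stray misprint. That would still disagree with the other four statements, since 2 × 600 = 1,200 mg/day.
- The note might be superseded text. It is not: it stands in the current Section 5.2.

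So four statements agree on 600 mg BID, and one gives 800 mg BID. Three of the four name Days 2-10. The fourth, the Treatment Regimen row, refers to the maintenance dose, which that row starts on Day 2 of a 10-day course.

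**Inputs.** Loading dose 1800 mg BID on Day 1; standard maintenance 800 mg BID; Child-Pugh A maintenance 600 mg BID; maintenance Days 2-10, which is 9 days; 200 mg tablets (6.1).

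**The plan's own figure.** 2 × 800 = 1,600 mg/day, matching the synopsis.

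| Quantity | Dosed from the 5.2 note | Dosed from 6.1 | Difference |
|---|---|---|---|
| Tablets per maintenance dose | 800/200 = 4 | 600/200 = 3 | 1 |
| Maintenance per day | 2 × 800 = 1,600 mg | 2 × 600 = 1,200 mg | 400 mg |
| Days 2-10 | 9 × 1,600 = 14,400 mg | 9 × 1,200 = 10,800 mg | 3,600 mg |
| Day 1 loading | 2 × 1800 = 3,600 mg | 3,600 mg | 0 |
| Full course | 18,000 mg | 14,400 mg | 3,600 mg |

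Relative excess in maintenance: 1,600/1,200 = 1.33, or 33%. Over the full course: 18,000/14,400 = 1.25, or 25%. The second figure is smaller because none of the Child-Pugh A statements reduces the loading dose. Seen from the standard dose, the intended reduction is 400/1,600 = 25%, and the note delivers 0%.

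**Would Section 6.6 catch it?** Its test is whether the dose exceeds what the document describes. For a Child-Pugh A patient the document now describes both 600 and 800 mg BID, so 800 mg does not clearly exceed it. Once the note is corrected, 800 mg BID clearly would.

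**The case against.** The best defence is that the error corrects itself. One parenthetical remark in an eligibility list disagrees with four concordant statements, including Section 6.1, where a dose should be looked up. The word *decreased* and the misprint BIID both signal a slip, and the intended value is not in doubt. Section 7.1 sends staff to 5.2 to check eligibility, not to set a dose. Under 6.5, outpatient dispensing follows separate pharmacy instructions. Placebo patients are unaffected. Chemistry on Days 5 and 10 and the liver-related stopping limits apply in any case.

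Most of this stands, and it keeps the risk small. It does not make the note harmless: this is operative text giving a wrong dose for patients who can be enrolled, and Section 6.6 is unclear for as long as the note remains.

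A reader might also infer that the note opens a gap in Section 8.7, which defines overdose by the highest daily dose in the document. The documents do not support that. The limit is 2 × 1800 = 3,600 mg/day, so 1,600 mg/day falls below it whether or not the note is corrected. That is a feature of 8.7, not a consequence of the note.

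**Conclusion.** The note in 5.2 is wrong as written and should be corrected to 600 mg BID. The size is 400 mg/day per affected patient, 3,600 mg over Days 2-10: 33% more maintenance drug, 25% more over the course. These figures assume a favipiravir-arm Child-Pugh A patient who takes every dose as the note states it.

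The likelihood is low or unknown. Section 6.1 is correct, the pharmacy instructions are not among the documents, and the number of Child-Pugh A patients is not given.

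A reader might go further and infer that patients were misdosed, that toxicity would follow, or that the intent-to-treat comparison is biased. The documents support none of these: they show no misdosed patient, give no pharmacokinetic data in hepatic impairment from which to judge the added exposure, and analyse efficacy by assigned arm.

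**What to change.** In Section 5.2, criterion 9, change the note to 600 mg BID on Days 2-10, or replace it with a reference to Section 6.1. The second option leaves one statement fewer to keep in step. Tell the sites, and confirm that the pharmacy instructions say 600 mg BID (3 tablets per dose). A check of doses already dispensed is needed only if those instructions turn out to say 800 mg; pharmacy can do it without unblinding site staff. The cost is one corrected number, IRB approval of the amendment and a letter to sites, with no added procedures or patients.

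A separate minor item can go into the same amendment. The synopsis and the body also differ on three other values:

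- **Respiratory limits:** the synopsis defines distress from RR 24 and HR 110 upward; 5.1 requires RR at most 20 and HR at most 100. RR 21-23 and HR 101-109 are unsettled.
- **Alcohol or drug abuse look-back:** two years in the synopsis, 6 months in 5.2.
- **Day 1 second dose:** 8-12 hours in the synopsis, 10-16 hours in 6.1.

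The documents do not show which values are intended, so the sponsor must decide. A reader might take 5.1(2a) to be written backwards because it lists normal values. Its parenthesis reads naturally as defining the absence of respiratory distress, so only the cutoffs need reconciling. These differences add nothing to the weight of the dosing point.
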